The intervention is novel in that it provides structured nursing assistant visits to nursing home patients during a short period of high delirium-risk, namely during acute illness and for 1 week after recovery, as a supplement to (not replacement for) standard care. This approach addresses the difficulty of targeting delirium prevention efforts during a nursing home stay that can span weeks, months, or years. We chose HELP as a model for our intervention in part because studies show that setting-specific adaptations to the model can be made across multiple domains, including enrollment criteria, screening and assessment tools, and intervention protocols, while remaining effective.⁵⁰⁻⁵² *With input from medical and nursing long-term care experts, we adapted the HELP intervention to be delivered by a dedicated, mobile CNA, as opposed to existing nursing home staff, and instead of trained volunteers (as in HELP), whose availability is uncertain in nursing homes and with whom safety may be a concern working with very frail disabled older adults. CNAs are already integral care team members in the nursing home and have the skills to deliver intervention components with a small amount of additional training. A dedicated staff that is mobile between units also allows a shift in care intensity to nursing home patients when they need it -- i.e., when they develop an acute illness. In general, unit nursing staff, in a fixed staff-to patient ratio, cannot shift to provide the level of intervention intensity (1-2 visits daily, 30 minutes each) likely needed to prevent delirium.¹⁹ Attention to other patients or tasks may be reduced. In addition, this role has precedence in the nursing home setting in such roles as CNA champions (e.g., oral care or falls specialists⁵³⁻⁵⁴) and rehabilitation or recreation therapists. We designed protocols to avoid inappropriate overlap with daily nursing activities by open communication between the intervention CNA and unit-based staff -- to tailor visits and ensure safety. Finally, although the CNA documents activities in the chart, s/he does not provide didactic or consultative advice. Our intervention also provides a potential career or training track for CNAs to gain specialized expertise that they bring to their unit or across units and an opportunity for promotion.*

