The PI has conducted innovative research to improve care in nursing homes, including interventions with CNAs, that has been widely cited and adopted.^{28, 59-60} He has worked with nursing homes in New York and nationally to implement innovative models of care. [name] (co-investigator) is the developer of HELP and the Confusion Assessment Method measure, and brings practical clinical trial experience.^{19, 57} [name] (Data Coordinating Center lead) has extensive experience in nursing home based research, measurement, and oversight of analyses from clinical studies.⁶¹ Advisory group members have been selected who provide expertise in the areas of delirium ([name]), nursing home ([name]), and long-term care nursing ([name]).

C. APPROACH

C.1 Overview. We propose to perform a controlled trial of a multicomponent intervention to prevent delirium at a large nursing home in New York City. The trial will be randomized by unit and evaluator-blinded. We will randomly assign 17 long-term care units to intervention or control and screen nursing home patients on each unit who experience onset of an acute change in condition according to established criteria and enroll 306. Those assigned to intervention (n=153) will receive daily visits from a mobile CNA trained to provide services to counter established risks for delirium, including dehydration, immobility, cognitive impairment, undernutrition, and sleep problems, for the duration of the acute illness and for 1 week following, in collaboration with the patient's primary medical and nursing team. Patients assigned to control (n=153) will receive usual care from the unit-based team. Delirium will be assessed 5 days a week by a research assistant (RA) blinded to study hypotheses and group assignment. Cognitive and physical function decline and hospital transfer will be ascertained during a 1 month follow-up period. We will conduct analyses to compare outcomes between intervention and control, as well as examine associations between outcomes and intervention features such as number and duration of visits. We will use regression models to adjust for covariates and effects of clustering.

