C.2 Patient identification and enrollment. Patients on one of 17 long-term care units at Jewish Home Lifecare (JHL) in the Bronx will be screened for onset of acute change in condition by case-finding and referral, according to previously reported methods:^{18, 49} an RA will review daily medical and nursing notes in the facility's electronic medical record for individuals with significant new symptoms or diagnosis requiring evaluation (e.g., labs), monitoring (e.g., vital signs), and/or treatment (e.g., antibiotics). In addition, the RA will accept telephone or in person referrals from unit-based medical and nursing staff who have been briefed on the requirements of the study. Nursing home patients returning from the hospital after an acute illness will also be screened. Patients will be enrolled who fulfill the definition of an acute change in condition as described by the American Medical Directors Association guideline⁶² (Appendix 1), or who have been flagged by unit nurses for "24-hour report" meaning their acute change requires additional active monitoring by the unit team. *Change in condition criteria include symptom, vital sign, and exam findings that may be indicative of acute illness and are designed to be highly sensitive to assist nurses in triaging their alerts to medical providers. Patients on nurse's 24-hour report are those that nurses deem at risk and consequently receive additional nurse monitoring and documentation (e.g., not eating, after a fall, or with other new symptom).* Patients must also fulfill the following entry criteria: 1) anticipated nursing home stay of at least 2 months (i.e., not a short-stay, subacute patient, since subacute patients usually receive services that overlap with intervention components), 2) patient not receiving hospice care (since the intervention activities may not be consistent with the comfort care goals of hospice patients and might be burdensome), 3) patient passes a simple screen indicating he/she is verbal and able to follow simple commands (in order to be able to follow simple commands required to participate in intervention activities), and 4) patient and/or legal surrogate provides assent to participate. In our prior experience the frequency of exclusion of non-subacute patients by reason was: 3% hospice, 4% nonverbal, and 3% refusal. We have received JHL IRB approval for a modified consent process that allows patients and surrogates to assent to participate (as opposed to sign consent) because of the low risk of the intervention, the need to initiate the intervention immediately after a change in condition starts, and delays associated with obtaining written consent from patients or legal surrogates (see Human Subjects Section; IRB approval letter). *For this revision we collected pilot data to ascertain the sensitivity of our approach to identifying patients. Among 113 patients in 1 month who had a definite acute illness as defined as receiving IV or antibiotics or being sent to the hospital (gold standard), there was 1 patient who was not captured by change in condition criteria or 24-hour report, for a capture rate of 99.1% (95%CI 97.4-100). In 39 (34.5%) of cases, the change in condition preceded receipt of IV, antibiotics, or hospital transfer by a range of 1-11 days, which provides an opportunity to provide delirium risk reduction components before a definitive diagnosis or treatment begins.*

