
C.3 Assignment by unit. This is a cluster randomized trial; units will be assigned to intervention or usual care arms. This design will prevent a unit from having patients in both groups and the likelihood of contamination.

Prior to initiating study enrollment, a biostatistician from the Data Coordinating Center (DCC, at a separate location) will assign units to intervention or usual care using a SAS macro. Units are uniform (e.g., there are no specialized dementia units) except that 1) 1 unit has equipment and programs for visually impaired, and 2) some units are larger (38-42 beds) than others (34-35 beds). Thus, the randomization procedure will maintain approximate balance by randomly assigning 5 larger and 3 smaller units to one arm and 4 larger and 5 smaller units to the other. Each unit will keep its assignment for the duration of the study. With rolling enrollment and a planned sample size of 306 we anticipate enrolling approximately 18 patients per unit (mean cluster size = 18).

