Dehydration	Hydration protocol: two 6-ounce cups of fluid by mouth daily	All patients except if not indicated as per nursing or medical team; e.g., those with congestive heart or renal failure with or at risk for fluid overload	1) Dehydration is delirium risk factor ^{64, 66} 2) Hi pulse & low BP assoc w/delirium ⁶⁵ 3) Rehydration may be effective ^{19, 34}	86% (178 refusals; 80 off floor or unavailable; 25 medical contraindicat)
Undernutrition	1) Provision of snack 2) Meal assistance	All patients receive snack unless 15 min before or after a meal	Undernutrition associated with delirium ⁶⁷	70% (385 refusals; 81 off floor or unavailable)
Sleep/relaxation	Sleep and relaxation protocol: massage, warm drink, quiet music	Patients who report sleep difficulties to intervention team	Avoiding sedative effective ¹⁹	80% (34 off floor /unavail; 12 time limit)
Medications	Medication alerts to medical team of meds associated w/delirium	All patients.	1) AGS criteria meds assoc w/ delirium ⁶³ 2) Med review effective ³⁵	--

*Per visit adherence data during 2434 visits, with top reasons patient did not receive a component.

C.5 Outcomes and variables. For intervention and control patients, a trained RA will use the Confusion Assessment Method (CAM), a widely-used, validated measure,⁵⁷ to ascertain incident delirium each weekday during treatment of the acute illness and for 7 days afterward. Delirium severity will be ascertained using the Delirium Index (DI), which has been shown to be reliable in patients with and without underlying dementia and its validity tested in a nursing home population.^{6, 58} Cognitive and physical function will be ascertained using the nursing home Minimum Data Set (MDS) Cognitive Performance⁶⁸ and Activities of Daily Living⁶⁹ scales, and the Brief Interview of Mental Status⁷⁰ at illness onset and 1 month after illness onset. These scales have been tested in the nursing home population and they are performed quarterly in all Medicare-certified facilities, making it possible to collect values on these measures from the medical record and establishing a pre-acute

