illness baseline. The RA will collect data by medical record review on demographic and clinical characteristics, characteristics of the acute illness, delirium risk, and hospital use (Table 2). Spanish language versions of cognitive test items have been obtained from developers of the delirium and cognitive instruments whenever available. We have developed Spanish versions of other items by iterative translation and back-translation.

Table 2. Outcomes and variables

Data	Source	Instrument or Measurement	Frequency or time point
Outcomes			
Delirium and delirium severity	Research assessment	Confusion Assessment Method (CAM); ⁵⁷ Delirium index (DI) ⁵⁸	Weekdays during illness & for 1w after illness end
Cognitive functional decline	Medical record, research assessment	Minimum Data Set Cognitive Performance scale; ⁶⁸ Brief Interview of Mental Status ⁷⁰	Pre-illness assessment, illness onset, illness end, 1m after illness onset
Physical functional decline	Medical record, research assessment	Minimum Data Set Activities of Daily Living scale ⁶⁹	Pre-illness assessment, illness onset, illness end, 1m after illness onset
Hospital use	Medical record	Hospital admission	Between illness onset & 1m after illness onset
Descriptive			
Demographics	Medical record	Age, gender, race/ethnicity	Enrollment baseline
Chronic illness	Medical record	14 chronic conditions (count)	Enrollment baseline
Acute illness	Medical record	Diagnosis and severity (Severity Score ⁷¹)	Acute illness onset
Delirium risk	Medical record; research assessment	Delirium risk score (↓vision, cognitive impairment, severe illness, ↑BUN/creat) ⁹	Acute illness onset
Intervention components received	Elder Life Specialist visit form	Component implemented that was indicated; reasons not implemented	During acute illness (intervention group only)
Intervention "dose"	Elder Life Specialist visit form	Frequency (n) of Elder Life Specialist visits; duration (min) of visits	During acute illness (intervention group only)

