C.8 Data collection, blinding, and study monitoring. The RA will enroll patients and provide enrollment information to the DCC and PI. The PI will notify the intervention team of enrolled intervention patients. Follow-up data collection (Appendix 3) will come from facility electronic medical record and MDS, patient observation, patient interview -- for which there are English and Spanish script versions -- and staff interview. The RA will be English/Spanish bilingual and will be trained 1) on the content and coding of each data element, data handling procedures, and protocols to handle possible problems and 2) in interview skills and referral procedures for participants who indicate symptoms that might require immediate medical assistance. The RA will enter data into protected computer files with software that contains edits for out-of-range entries, to prompt correction. Data are in password-protected, encrypted environments and are made available to the analytic programmers through a secure file-sharing website. *To maintain RA blinding we will 1) assign the RA to supervision by a different department (the research department) from intervention staff (nursing department), 2) keep the RA and intervention staff unaware of each others' presence and roles, 3) keep the RA and intervention staff unaware of study aims and hypotheses, and 4) schedule separate intervention and RA shifts on the units to avoid overlap on a unit at the same time. At study end we will test for blinding success by asking the RA to guess intervention and control assignments.* The PI will provide oversight of study activities and blinding activities following Jewish Home Lifecare IRB committee requirements to ensure study safety. A 3-person advisory group meeting every 4-6 months will provide guidance on data and safety issues, decisions and challenges to study implementation, intervention refinement, and disseminating results.

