C. 9 Strengths and limitations Study strengths are its innovative intervention, the clinical importance of delirium in this setting, the expertise of the investigators, and pilot work that supports study feasibility. Study limitations include the single site, limiting general applicability, and the limited sample size, limiting power to address all important outcomes. However, if this study is positive, it lays the groundwork for a future study that is multi-site that can produce information on additional outcomes and cost. The study is also important if no effect is observed, or if it yields findings on components that suggest a need to modify the intervention.

Workplan and timeline (All steps to be overseen by [name], w/input by [name], [name], and advisory group)

Study Activities	Project Year Year Month Starting	1		2		
		2015		2016		2017
		Apr	Jun	Jan	Jul	Jan
Hire and train RA and intervention CNAs ([name], Data Coord. Cent.) (3 mo)		XXX				
Establish protocols, randomly assign units ([name], [name], DCC) (3 mo)		XXX				
Enroll patients, provide intervention, collect /enter data (RA, CNAs, DCC) (19 mo)		XXXXX	XXXXXX	XXXXXX	XX	
Analyze data, including interim safety analysis (adv grp, [name], DCC) (4 mo)				X		XXX
Reports, dissemination, next grant preparation ([name], [name], [name]) (3 mo)						XXX

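### No C.8 blinding step covers the medical record: if the intervention CNA's chart entries are visible and recognisable to the RA who rates the CAM, they can reveal a unit's arm

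*Combined protocol and SAP*

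**What the plan says.** **Blinding promised.** C.1: "Delirium will be assessed 5 days a week by a research assistant (RA) blinded to study hypotheses and group assignment".

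**Blinding steps.** C.8 lists four: separate departmental supervision (research for the RA, nursing for intervention staff); "keep the RA and intervention staff unaware of each others' presence and roles"; neither party knows the aims or hypotheses; and separate shifts on the units. At study end the RA is asked to guess the assignments.

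**What the CNA writes.** B.2, in describing the CNA's role: "although the CNA documents activities in the chart". C.4 and Table 2 also name a visit form, the source for components received and dose. The text does not say whether the form is part of the chart.

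**What the RA reads.** C.2: "an RA will review daily medical and nursing notes in the" facility's electronic record, to find acute changes in condition. C.5: "The RA will collect data by medical record review on demographic and clinical characteristics", and on acute illness, delirium risk and hospital use. C.8 names the electronic record as a source of follow-up data.

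**Who rates delirium.** C.5 gives the weekday CAM to a trained RA. C.8 speaks of the RA in the singular, and the workplan entry is "Hire and train RA and intervention CNAs", with one RA beside several CNAs.

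**Allocation.** C.3: "Each unit will keep its assignment for the duration of the study".

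**The concern.** Step 2 of C.8 states a goal. Step 4 gives it a physical means, because the two parties do not meet on a unit. Nothing in the supplied text gives it a means in the record, where the CNA writes and the RA reads.

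Allocation is by unit and never changes. An RA who recognises intervention entries for one patient therefore learns the arm of every later patient on that unit, about 18 in all. The CNA and the unit staff cannot realistically be blinded, so the rater's blinding is the main protection against detection bias in the CAM outcome.

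**Working it through.** The plan gives no figure on this point to reproduce. The check is a reading of the sections against each other, followed by two calculations for scale.

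**1. Do the two activities overlap in time?** CNA visits run through the illness and 7 days beyond (C.4). CAM ratings run on weekdays over the same window (C.5). Case-finding is daily on all 17 units (C.2). The RA is therefore reading records while ratings are in progress. Illness end, which sets the last rating day, is defined by treatment or monitoring (C.4), so the record is probably consulted for that too.

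**2. Does any C.8 step cover the record?**

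| C.8 step | Limits contact through | Covers chart entries? |
|---|---|---|
| 1 Supervision | Line management | No |
| 2 Mutual unawareness | Goal only | No means stated |
| 3 Aims and hypotheses | Knowledge of what is expected | No |
| 4 Separate shifts | Meeting on the unit | No |

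**3. How much could there be to see?** Inputs: 153 intervention patients (C.1), 14.2 visits per episode in the pilot (B.4), 8 or 9 intervention units (C.3), mean cluster size 18 (C.3).

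- Total visits: 153 × 14.2 = 2,173.
- Per intervention unit: 2,173 / 9 = 241 or 2,173 / 8 = 272. Control units have none.
- First nine patients on a unit: 9 × 14.2 = 128 visits.

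One chart entry per visit is an assumption.

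**4. Illustration of error, assuming no true effect.** Let p be the delirium rate, f the share of intervention patients rated after the RA recognises the arm, and u the share of their true cases then missed. The values of f and u are chosen; the documents give none. f = 0.5 means recognition after 9 of 18 patients, and f = 0.25 after 13 to 14. Effective n per group is 150 / 1.17 = 128 (C.6).

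The observed intervention rate is p₂ = p(1 − f·u), and d = p − p₂. With p̄ = (p + p₂)/2, SE₀ = √(2p̄(1 − p̄)/n) and SE₁ = √([p(1 − p) + p₂(1 − p₂)]/n):

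error = Φ((d − 1.96·SE₀)/SE₁) + Φ((−d − 1.96·SE₀)/SE₁)

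Example with p = 0.35, f = 0.5, u = 0.20: p₂ = 0.315, d = 0.035, SE₀ ≈ SE₁ ≈ 0.0588, error = 0.086 + 0.005 = 9.1%.

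| p | f | error, u = 0.10 | error, u = 0.20 |
|---|---|---|---|
| 35% (C.6) | 0.25 | 5.2% | 6.0% |
| 35% | 0.5 | 6.0% | 9.1% |
| 22% (pilot, B.4) | 0.25 | 5.1% | 5.5% |
| 22% | 0.5 | 5.5% | 7.2% |

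**5. Repeated ratings.** C.6 counts delirium at any time in the illness period, so a case is lost only if every positive rating is missed. If misses are independent over k positive ratings, each must be missed with probability u^(1/k). For u = 0.10 or 0.20 that is 32% or 45% at k = 2, and 63% or 72% at k = 5. If misses are fully correlated, 10% or 20% is enough. The lower error figures are therefore more plausible.

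**6. Bias in the other direction.** Suppose the truth is 35% against 18% and cases are missed on control units instead. Power on the same simple test, before the plan's continuity and reliability adjustments, falls from 87% to 84% or 80% (f = 0.25, u = 0.10 or 0.20) and to 80% or 71% (f = 0.5).

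**The case against.** The key link is not in the text. Nothing says that CNA entries sit among the notes the RA opens. B.2 mentions the chart in passing, and the trial's own visit data go on a separate form. Appendices 2 and 3 are cited but were not available, and either could hold an access rule. This stands, and it is why the point is conditional and limited to the supplied text.

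Harm also needs several further steps. The entries must be recognisable to an RA who is not told of the intervention roles. The RA must link them to an arm and then, without knowing the hypothesis, rate differently. B.2 notes that comparable roles already exist in nursing homes, so an entry about a snack or a walk need not look like a trial arm. This stands as a reason to expect a small bias. It does not deliver what C.1 promises, which is blinding to assignment as well as to hypotheses.

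The guess at study end can show that blinding failed, but it cannot repair the ratings.

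A reader might infer that the RA will certainly be unblinded, or that the plan contradicts itself. The documents do not support that, because the location and visibility of CNA entries are not stated. A reader might also assume that every intervention patient is rated unblinded, which would give much larger error rates. Nothing in the documents supports that assumption either.

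**Conclusion.** The point holds as a conditional gap. In the supplied text no blinding step covers the medical record, although a member of the nursing department charts intervention activity and the RA reads nursing notes daily. If those entries are visible and recognisable, they can reveal a unit's arm to the rater of the Aim 1 primary binary outcome.

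The conclusion rests on three readings: that one RA both reviews records and rates the CAM (natural from C.5, C.8 and the workplan, but not stated outright); that CNA entries appear in what the RA reads (not stated); and that the missing appendices do not already prevent this.

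The size and direction of any bias cannot be determined from the documents. The error and power figures show scale under chosen inputs and are not estimates. The gap is worth closing before enrolment because the remedy is cheap and biased ratings cannot be corrected afterwards.

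**What to change.** Add a fifth step to the list in C.8, for example:

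> Intervention CNA chart entries are kept in a note type or location that unit clinical staff can see but that the RA's login does not display. Visit components and dose are recorded on the visit form, which the RA does not see.

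If the record cannot restrict access, intervention staff keep the detail on the visit form. Any chart entry then uses neutral wording that does not identify the study role. This is weaker, because such entries would still appear only on intervention units.

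Either way, unit staff must still see what they need, because B.2 relies on open communication to tailor visits and keep them safe. Keep the arm guess at study end. If Appendix 2 or 3 already keeps CNA entries out of the RA's view, a cross-reference in C.8 is enough.

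Two tempting additions are best left out. Writing the exclusion into the RA's own review procedure would tell the RA that such entries exist, contrary to step 2. Asking unit staff not to mention CNA visits would either advertise the intervention to control units or make the staff briefing differ by arm.

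Cost: a small record-configuration task and one added step in the protocol. The visit form already exists and no new staff are needed. Some leakage would remain through unit nurses' own notes, staff referrals and interviews, and patients who mention the visits.

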B.4 Preliminary studies. In addition to studies establishing our enrollment and assessment procedures,^{18, 49} we have conducted preliminary studies to demonstrate the feasibility of intervention procedures and acceptance by nursing home staff.²⁰ *First, we developed standardized procedures and training (Appendix 2) in collaboration with a HELP Center of Excellence. At start up and thereafter we instituted a weekly whole-team rounds and discussion of each patient to optimize intervention fidelity.* In 2013 we implemented the intervention during 149 acute illness episodes at the study site, for a rate of 14 per month. 63% of patients were female, 37% Spanish-speaking, with average age of 83 years. The mean Brief Interview of Mental Status score was 7.5 (max possible score 15), indicating moderate cognitive impairment. The most common illnesses initiating receipt of the intervention were infections of bladder (29%), lower respiratory tract (18%), and skin (10%). Intervention CNAs delivered on average 14.2 visits over a 13.5 day span per episode, with average visit length of 30.5 minutes. Patient adherence to each of the components per visit ranged from 70-94% (Table 1), with a goal of 75%. The most common reasons for not receiving a component were patient refusal and patient off floor or unavailable. In a semi-structured interview of 28 patients who were capable of providing feedback, 27 had high satisfaction with the intervention and endorsed the value of each intervention component. *On days when 2 CNAs visited the same patient (n=179), percent agreement on provision of the key intervention components (orientation, mobility, fluids) was high, ranging from 80-93%, indicating excellent fidelity.* Among 4 physicians and 13 unit nursing staff who participated in a semi-structured interview, all indicated that communication between unit and intervention staff was effective and 14 endorsed that work stress was lower with the intervention, indicating good integration between intervention and unit nursing activities. *Staff*

indicated that they appreciated and recognized the intervention CNA as a mobile staff member who delivered focused services to patients on the floors, but not daily care. Delirium occurred during 22% of acute illnesses and 5% of patients were transferred to the hospital during or within 30 days after finishing the intervention.²⁰

B.5 Investigative team

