C.4 Intervention and control. Residents with acute illness on intervention units will be seen by an intervention CNA at least once daily 7 days a week. The CNA will be English/Spanish bilingual and will provide intervention components as shown in Table 1 guided by structured protocols and a daily visit form (Appendix 2). A typical visit lasts 30 minutes and begins with an introduction and orientation activity followed by provision of water, a reminiscence activity or game, a physical exercise, and a snack and second cup of water. Patients may also receive a relaxation visit at night and given a warm drink, a hand or foot massage, and quiet music. Daily visits will last for the duration of the illness and 7 days following the illness end. Illness end is defined as the last day of illness treatment (e.g., last day of antibiotics) or monitoring (e.g., last day on nursing “24-hour report”). Seven day a week coverage, provided by 1.4 FTE CNAs, is important for this intervention since it is a relatively brief (e.g., 2 week) intervention. Medication review using American Geriatrics Society Beers criteria⁶³ for drugs associated with delirium will be semi-automated and alerts provided to the primary team by secure messaging or telephone. During weekly intervention staff meetings patients in the intervention group will be discussed with the primary medical and nursing team. The planned intervention group sample size results in a caseload of 4-8 patients seen daily, which is well within the workload capacity of the intervention CNAs. Patients with acute illness on control units will be cared for as usual by the primary nursing home nursing and medical staff.

Table 1. Intervention components: all components delivered by the CNA except for medication alerts

Risk Factor	Intervention	Recipients / Tailoring	Evidence	Adherence*
Cognitive Impairment	1) Daily visit & orientation activity 2) Therapeutic activity: reminiscence, reading, music, pictures	All patients.	1) Cognitive impairment is delirium risk factor ⁸⁻¹⁰	94% (79 off floor or unavailable; 23 refusals)
Immobility	Mobilization protocol performed to patient's maximum ability: 1) chair stands 2) walking 3) range of motion	All patients. Patient's maximum determined by intervention CNA from chart, patient and staff report, and observation	1) Early mobilization effective ¹⁹ 2) NH delirium assoc w/restraints ⁶⁴ 3) Delirium assoc w/fall ⁶⁵	77% (382 refusals; 80 off floor or unavailable)

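### The blinding steps act only on staff: none covers what a visited patient may tell the rater, and under unit assignment a remark can unblind later ratings on that unit

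*Combined protocol and SAP*

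**What the plan says.** On the rater, C.1 states: "Delirium will be assessed 5 days a week by a research assistant (RA) blinded to study hypotheses and group assignment". C.5 has the research assistant (RA) use the Confusion Assessment Method (CAM) "to ascertain incident delirium each weekday during treatment of the acute illness and for 7 days afterward". Table 2 gives the Delirium Index (DI) the same schedule. C.8 lists the data sources, which include "patient interview -- for which there are English and Spanish script versions -- and staff interview".

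On the intervention, C.4 says that patients with acute illness on intervention units "will be seen by an intervention CNA at least once daily 7 days a week", for the illness and seven days after it. The RA's assessments and the nursing assistant's (CNA's) visits therefore fall in essentially the same window. C.2 admits only patients who are verbal.

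On blinding, C.8 lists four steps:

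1. The RA and the intervention staff are supervised by different departments.
2. Each is kept unaware of the other's presence and role.
3. Both are kept unaware of aims and hypotheses.
4. The plan will "schedule separate intervention and RA shifts on the units to avoid overlap on a unit at the same time".

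At study end the RA guesses the assignments.

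On assignment, C.3 says that no unit has patients in both arms and adds: "Each unit will keep its assignment for the duration of the study".

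**The concern.** The patient meets both the CNA and the RA, and can carry information from one to the other however well the staff are separated. Step 2 states the aim that the RA should not know of the intervention staff, but gives no means that reaches the patient.

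The cluster design raises the stakes. In a trial randomised by patient, a remark would expose one assignment. Here, an RA who connects a remark with the unit can carry that knowledge to later ratings there, including those of patients not yet enrolled. The leak is also one-sided, because control patients have no CNA visits to mention.

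CAM and DI both involve rater judgement. If the RA came to expect benefit, ratings on exposed units could drift in favour of the intervention, and the protection claimed in C.1 would weaken as enrolment goes on.

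**Working it through.** **The plan's own figure.** C.3 gives a mean cluster size of 18: 306 / 17 = 18.0, which reproduces. C.6 gives a variance inflation factor of 1 + (18 − 1) × 0.01 = 1.17, which also reproduces.

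**Do the C.8 steps reach the patient?** Supervision, mutual unawareness and separate shifts concern the RA and the intervention staff. Unawareness of aims and hypotheses concerns what those two groups are told. None asks patients or families to say nothing about their care, and none says what the RA does after hearing something. The guess at study end has no date attached, so it cannot show which ratings were affected.

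**Can patients describe the visits?** Some can. In the pilot (B.4), among 28 patients capable of giving feedback, "27 had high satisfaction with the intervention and endorsed the value of each intervention component". That was an interview about the intervention, so it shows recall is possible but gives no rate of unprompted remarks.

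**Number of contacts.** B.4 reports: "Intervention CNAs delivered on average 14.2 visits over a 13.5 day span per episode". If that span holds in the trial:

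- weekday RA contacts per patient = 13.5 × 5/7 = 9.64
- contacts per unit = 18 × 9.64 = 173.6, about 174

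**Chance that a unit is revealed.** Let q be the chance that one contact yields a revealing remark that the RA recognises. The documents give no value for q, so a range is assumed. Contacts are treated as independent with equal q, and patients as enrolled one after another.

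- per patient: p = 1 − (1 − q)^9.64
- per unit by the end: 1 − (1 − p)^18
- mean share of a unit's patients enrolled after an earlier patient's remark: the average over k = 0 to 17 of 1 − (1 − p)^k

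| q (assumed) | p | Unit revealed by end | Share enrolled afterwards |
|---|---|---|---|
| 0.1% | 1.0% | 16% | 8% |
| 0.5% | 4.7% | 58% | 32% |
| 1% | 9.2% | 83% | 50% |

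C.3 puts 8 units in one arm (5 + 3) and 9 in the other (4 + 5). Multiplying 8 and 9 by the third column gives about 1.3 to 1.4, 4.6 to 5.2, and 6.6 to 7.4 intervention units revealed.

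**What it could do to the test (illustration only).** Assume no true effect, 35% delirium in both arms (the C.6 baseline), and 153 per arm deflated for clustering: 153 / 1.17 = 130.8. Suppose that an unblinded RA misses a fraction u of cases in a share s of intervention patients. The observed intervention rate is then 0.35 × (1 − s × u). Two-sided error at nominal 5%, by the normal approximation for two proportions:

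- s = 0.5, u = 0.2: 0.35 × 0.90 = 31.5%; error about 9%
- s = 1, u = 0.2: 0.35 × 0.80 = 28%; error about 23%

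Both s and u are assumptions. Nothing in the documents says that the RA would under-call at all.

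**The case against.** Four arguments on the other side have weight.

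- **Step 3 targets the mechanism.** Bias needs a rater with an expectation, and the RA is to be kept unaware of aims and hypotheses. This stands as a real mitigation. It is incomplete, because reports of visits from some units and never from others could still show the pattern.
- **A remark may mean nothing to the RA.** Visits consist of water, a snack, an activity and exercise (C.4). B.2 describes CNAs as part of the ordinary care team and mentions recreation therapists. The documents do not say whether the RA knows that assignment is by unit. This stands: a remark can unblind, but need not.
- **Many patients will not recall visits.** The pilot mean Brief Interview of Mental Status score was 7.5 of 15. This also stands. If remarks come mainly from a few able patients, the table overstates the share of units revealed for the same average q.
- **An instruction may exist elsewhere.** Appendix 3 and the Human Subjects section are not in the supplied text, and C.8 says the RA is trained in interview skills and in handling problems. An instruction there cannot be ruled out. If there is one, C.8 need only refer to it and add the recording of disclosures.

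A reader might go further and infer that one remark exposes all 18 patients on a unit. It cannot affect patients whose ratings are complete. A reader might also divide the 28 interviewed patients by the 149 pilot episodes and treat the result as the proportion able to disclose. B.4 does not say how many patients were approached, and it mixes patients with episodes, so no such rate can be derived.

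**Conclusion.** The gap holds in a limited form. In the supplied text, no blinding step covers what visited patients may say to the RA. Fixed assignment by unit means that a remark can unblind later ratings on that unit, on the intervention side only. The end-of-study guess may detect this but neither prevents nor dates it.

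The size is unknown. The range of 16% to 83% of intervention units revealed rests on assumed rates of 0.1% to 1% per contact, the pilot episode length, independent contacts, and an RA who recognises each remark. The documents do not support saying that the rater will be unblinded or that the delirium result will be biased. They do support saying that the blinding claim has an unprotected route that is cheap to narrow and, without dated records, hard to assess afterwards. It should be dealt with before enrolment starts.

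**What to change.** - **Scripts (C.8, English and Spanish).** Add one general neutral sentence, identical in both arms, asking patients and family not to discuss the care they receive. Word it without mentioning visits, so that it does not cue the RA. Instruct the RA not to ask about care.
- **Record.** Have the RA send the Data Coordinating Center a dated one-line note, in the same form for both arms, of any remark suggesting assignment. Report these by unit and date alongside the end-of-study guess.
- **Analysis (C.7).** Do not drop post-disclosure assessments from intervention units only. That would remove data from one arm, late in calendar time, and shorten the period in which delirium at any time during the illness (the C.6 definition) can be seen, artificially lowering the intervention rate. If a sensitivity analysis is added, select whole patients by enrolment date with the same calendar cut-off in both arms, such as the first recorded disclosure or a set date. Label it exploratory.

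The cost is one script sentence, a short log and, if wanted, one extra analysis on fewer patients. No staff or visits are added. The sentence will not work for every cognitively impaired patient, and it and the log may slightly raise the RA's awareness. The script sentence also does not close other routes: the CNA charts activities (B.2), an RA reads nursing notes daily (C.2), and staff are interviewed (C.8).
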